2.7.2.3 Analyses of neurological assessments

Analysis will be based on FAS using observed data.

Number and percent of patients will be provided by cohort and treatment group for the following neurological events related to severe malaria:

- Convulsion developing or persisting > 6 hour after the IV study treatment; where “persisting ” means that convulsion is present at baseline and reoccurred after IV study treatment.
 - Moderate or severe neurological sequelae for each individual function domain and overall as assessed by investigator (Refer to [Appendix 5, Section 5.1](#)).
 - Overall moderate or severe neurological sequelae related to malaria episode at Day 29 confirmed by adjudication.

Following neurological examination results will be listed and summarized descriptively by visit, cohort, and treatment group.

- Type of convulsion
- Presence of ≥ 2 episodes of convulsions excluding febrile seizures during last 24 hours

- Any episode of convulsion lasting for ≥ 15 minutes
- Cranial Nerve Palsy
- Motor systems: Posturing, cerebellar ataxia, strength, Deep Tendon reflex, and tone
- Sense organs that characterize the vision, hearing, and speech

Neurological examinations are described in [Appendix 5, Section 5.1](#).

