1.2 Purpose

The purpose of this study is to identify safe and effective dose of intravenous cipargamin in moderately severe (Cohort 1) and severe malaria participants (Cohorts 2-5) in an age-descending manner (refer Barnes et al 2004 for definition of moderately severe malaria and Section 16.4 for the definition of severe malaria). The study also aims to evaluate clinical success as a novel clinical outcome endpoint, which will be implemented in the confirmatory Phase III study.

The purpose of Cohorts 1 and 2 will be to establish efficacy, PK and safety of IV cipargamin in participants aged ≥ 12 years. Two cipargamin dose regimens will be evaluated in each of Cohorts 1 and 2. Based on the data obtained, one IV cipargamin dose will be selected for pediatric participants in Cohorts 3-5. Participants aged from 6 months to <12 years will be dosed using weight bands and age-specific considerations.

2 Objectives and endpoints

All objectives and endpoints are in comparison of IV cipargamin to IV artesunate in participants with moderately severe or severe *P. falciparum* malaria.

Table 2-1 Objectives and related endpoints

Objective(s)	Endpoint(s)
Primary objective(s)	Endpoint(s) for primary objective(s)

 To assess the efficacy of IV cipargamin 	
 Proportion of participants with $\geq 90\%$ P. falciparum parasite reduction at 12 hours, see Section 2.1 for the primary estimand
Secondary objective(s)	Endpoint(s) for secondary objective(s)

 To assess clinical outcome 	
 Proportion of participants with clinical success (see Section 8.3.1.1.) over time. Clinical success at 48 hours is considered as the key secondary endpoint, see Section 2.2 for the secondary estimand.

 To assess the presence/absence of individual signs of severe malaria 	
 Proportion of participants with individual signs of severe malaria over time (see Section 8.3.1.2.).

 To assess the risk of hemolysis 	
 Proportion of participants developing hemolysis (early and delayed) after treatment (see Section 10.2.3)

 To assess the risk of long term neurological sequelae 	
 Proportion of participants with neurological sequelae at Day 29

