Based on the results from the neurological examination of every participant, neurological sequelae will be graded by the neurological sequelae adjudication committee. Further details about grading of neurological sequelae will be mentioned in adjudication committee charter.

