All analyses described below will be performed using the FAS without imputation for missing assessments, ie., missing assessments will be excluded from analysis.

For the following individual signs of severe malaria, the shift table of post-baseline presence relative to baseline presence or not will be provided by visit (24 hours, 48 hours, 72 hours, 96 hours, at hospital discharge, Day 6, Day 8, Day 15, Day 22, and Day 29), cohort, and treatment group:

- Altered consciousness - Prostration or GCS < 11 for age > 5 yrs / BCS < 3 for age ≤ 5 years
- Renal Impairment- Serum creatinine > 3 x ULN or > 3 mg/dL or need for renal replacement therapy
- Acidosis- Serum lactate > 4 mmol/L
- Respiratory distress – present or absent
- Severe anemia- Hb < 5 g/dl or Hb < 7g/dl in pediatric and adults respectively with parasite count of > 10,000/μl or need of blood transfusion
- Jaundice- Serum bilirubin > 3 g/dl with parasite count of > 100,000/μl
- Hypoglycemia- plasma glucose < 40 mg/dL

Number and percent of participants will be provided by cohort and treatment group for the following events related to severe malaria:

- Convulsion developing or persisting > 6 hour after the IV study treatment. Note: “persisting > 6 hour” means that convulsion is present at baseline and again at a visit that is > 6 hours after IV study treatment.
- New severe malaria signs (as per WHO severe malaria criteria) after the IV study treatment
- Neurological sequelae (by adjudication) at Day 29

Neurological Examination results will be summarized descriptively by visit, cohort, and treatment group.

For the following time to event variables, the first visit with the event will be used to calculate the time if a participant experiences the event. If a participant does not experience the event, the time will be censored at the last visit assessment for specific type of event (such as last sit assessment, etc.) with the exception of date of discontinuation (or death) for time to oral antimalarial therapy.

- Time to oral antimalarial therapy (in hours),
- Time to recover prostration in participants who are prostrated at baseline

Descriptive statistics will be provided using the Kaplan-Meier method and Kaplan-Meier curves will be presented by cohort and treatment.

Day of discharge from hospital will be summarized descriptively by cohort and treatment group. Day of death will be used in case of death during hospitalization.

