1.2 Study objectives and endpoints

Table 1-1 Objectives and related endpoints

Objective(s)	Endpoint(s)
Primary objective(s)	Endpoint(s) for primary objective(s)

 To assess the efficacy of IV cipargamin 	
 Proportion of patients with $\geq 90\%$ P. falciparum parasite reduction at 12 hours, see Section 2.5.1 for the primary estimand
Secondary objective(s)	Endpoint(s) for secondary objective(s)

 To assess clinical outcome 	
 Proportion of patients with clinical success (see Section 2.7.2.1) over time. Clinical success at 48 hours is considered as the key secondary endpoint, see Section 2.6.1 for the secondary estimand.

 To assess the presence/absence of individual signs of severe malaria 	
 Proportion of patients with individual signs of severe malaria over time (see Section 2.7.2.2).

 To assess the risk of hemolysis 	
 Proportion of patients developing hemolysis (early and delayed) after treatment (see Section 2.8.2)

 To assess the risk of long term neurological sequelae 	
 Proportion of patients with neurological sequelae at Day 29 (see Section 2.7.2.3)

 To evaluate parasite clearance dynamics 	
 Proportions of patients with $\geq 90\%$ parasite reduction at 24 and 48 hours PCE slope half-life Time to P. falciparum parasite clearance (PCT) P. falciparum parasite reduction ratios (PRR) at 12, 24 and 48 hours Proportion of patients with recrudescence and reinfection by Day 29 
See Section 2.7.2

 To assess other efficacy endpoints 	
 Time (days and hours) to switch to oral therapy Day of discharge from hospital Time (hours) to recover from prostration 
See Section 2.7.2

 To evaluate the safety and tolerability of IV cipargamin 	
 Standard safety/tolerability assessments (incidence of serious adverse events (SAEs), mortality, in-hospital mortality, adverse events (AEs), and routine safety and laboratory assessments) 
See Section 2.8

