5.1.1 Grading of neurological sequelae

Grading for individual domains:

Individual deficits for each neurological functional domain (motor, vision, hearing and speech) will be recorded on the CRF according to [Table 5-3](#). These deficits are pre-classified as moderate severe grades as per [Table 5-3](#). For e.g. if a patient is recorded with deficit of Monoplegia/paresis then grading of this deficit is moderate or if a patient is recorded with deficit of cranial nerve palsies then grading of this deficit is severe. Because the grading of individual deficits are fixed, these will not be captured in the clinical database but will be mapped to the their respective severity grades (moderate/ severe) according to [Table 5-3](#) at the time of statistical analysis.

Table 5-3 Grading of Neurological Sequelae

S.No	Neurological functional domain	Graded as Moderate	Graded as Severe
1	Motor		
a)	Monoplegia/paresis	X	
b)	Hemiplegia/paresis		X
c)	Quadriplegia/paresis		X
d)	Continued posturing		X
e)	Cerebellar Ataxia		X
f)	Cranial nerve palsies	X	
2	Vision		
a)	Blindness bilateral		x
b)	Blindness unilateral	X	
c)	Bilateral vision impairment	X	
d)	Unilateral vision impairment	X	
3	Hearing and Speech		
a)	Bilateral deafness		x
b)	Unilateral deafness	X	
c)	Bilateral hearing impairment	X	
d)	Unilateral hearing impairment	X	
e)	Speech difficulties	X	

S.No	Neurological functional domain	Graded as Moderate	Graded as Severe
f)	Unable to speak		X
4	Convulsion		
a)	Any convulsion In patient with no history of convulsion	X	
b)	Status epilepticus		X

Overall grading of neurological sequelae:

Overall grading for neurological sequelae will be derived using individual grading as mentioned above.

Following algorithm will be used to determine the overall grading of the neurological sequelae.

- A patient with at least 1 severe deficit in any functional domain, the overall grading will be severe.
- A patient with at least 1 moderate deficit in 2 or more functional domains, the overall grading will be severe.
- A patient with at least 1 moderate deficit in any one functional domain, the overall grading will be moderate.
- In case the medical history CRF mentioned a pre-existing neurological problem and there is no significant deterioration of symptoms during the malaria episode, the neurological problems will not be considered as being sequelae of the acute disease episode. This evaluation will be performed by the Adjudication committee.

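### The Day 29 neurological sequelae summary has no stated denominator and no rule for participants who die first, so the arm with more deaths can show the lower percentage

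*SAP*

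**What the plan says.** Protocol Table 2-1 has a secondary objective on the risk of long-term neurological sequelae. Its only endpoint is "Proportion of participants with neurological sequelae at Day 29". The introduction to Protocol Section 2 says that all objectives and endpoints compare IV cipargamin with IV artesunate.

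On scoring, Protocol 8.3.1.3 says: "Based on the results from the neurological examination of every participant, neurological sequelae will be graded by the neurological sequelae adjudication committee". SAP 5.1.1 adds: "Overall grading for neurological sequelae will be derived using individual grading as mentioned above". The grades are moderate and severe, built from examined deficits. There is no category for death.

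On analysis, SAP 2.7.2.3 says: "Analysis will be based on FAS using observed data". It then plans number and percent by cohort and treatment group for "Overall moderate or severe neurological sequelae related to malaria episode at Day 29 confirmed by adjudication". Protocol 12.5.1 introduces the block that contains adjudicated Day 29 sequelae with: "All analyses described below will be performed using the FAS without imputation for missing assessments, ie., missing assessments will be excluded from analysis".

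The time point and analysis set vary between places:
- SAP 2.7.2.3 and both objectives tables say at Day 29.
- SAP Table 2-11 says by Day 29.
- The endpoint list in Protocol 12.5.1 says Day 2.
- SAP 2.7.2.3 uses the FAS, whereas the sequelae row of SAP Table 2-13 (DMC and interim outputs) uses the Safety set.

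**The concern.** A participant who dies before Day 29 cannot be examined at Day 29. Under the protocol's exclusion rule that participant leaves the analysis, so the percentage describes only those who lived to be examined. Survival is itself an outcome of treatment. If one drug keeps alive more patients who then have deficits, it can look worse on this endpoint. If it loses them, it can look better.

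The plan handles death explicitly elsewhere. Death before the 12-hour count is a non-response (SAP 2.5.3). In-hospital and malaria-related deaths are clinical failures (Protocol Table 8-3). Day of death stands in for discharge day when a patient dies in hospital (SAP 2.7.2.5). The sequelae endpoint has no such rule. At stake is a misleading ranking of the arms on the only endpoint for a named objective, in a table that also goes to the DMC and to the interim assessment after Cohort 2.

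**Working it through.** **Plan's own figure.** Neither document gives a rate, sample size or power for sequelae, so there is nothing to reproduce for this endpoint. The pooled arm size in the count example below is the plan's 116 (6 + 14 + 38 + 38 + 20 = 116).

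**Model (all rates assumed).** Take two arms with the same underlying risk. A share H of each arm is high-risk, and all deaths come from that share. High-risk survivors have sequelae risk s_hi; everyone else has s_lo. Death rates are d_A = 5% and d_B = 10%. H is set to the larger death rate, 10%, and s_lo = 5%. For an arm with death rate d:

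- sequelae as a share of all participants: q = (H − d) × s_hi + (1 − H) × s_lo
- observed-data percentage: q / (1 − d)
- percentage with deaths kept in the FAS denominator as no sequelae: q
- death or sequelae: q + d

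**Arm B** (every high-risk participant dies): q = 0 + 0.90 × 0.05 = 0.045. Observed 0.045 / 0.90 = 5.0%; FAS denominator 4.5%; death or sequelae 0.045 + 0.10 = 14.5%.

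**Arm A:** q = 0.05 × s_hi + 0.045.

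| s_hi | q (A) | Observed, A vs B | FAS denominator, A vs B | Death or sequelae, A vs B |
|---|---|---|---|---|
| 5% | 0.0475 | 5.0% vs 5.0% | 4.8% vs 4.5% | 9.8% vs 14.5% |
| 20% | 0.0550 | 5.8% vs 5.0% | 5.5% vs 4.5% | 10.5% vs 14.5% |
| 50% | 0.0700 | 7.4% vs 5.0% | 7.0% vs 4.5% | 12.0% vs 14.5% |

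The first row is the case where death is unrelated to sequelae risk. The observed-data percentage is then undistorted, but a full FAS denominator still favours the arm with more deaths. In the other rows arm B looks better on observed sequelae and worse on death or sequelae.

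**Wider gap in deaths.** With 5% against 15% (H = 15%) and s_hi = 50%, q_A = 0.10 × 0.50 + 0.85 × 0.05 = 0.0925 and q_B = 0.0425. Observed: 0.0925 / 0.95 = 9.7% against 0.0425 / 0.85 = 5.0%. Death or sequelae: 14.3% against 19.3%.

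**In counts, 116 per arm (invented for illustration).** Six deaths and 8 with sequelae give 8/110 = 7.3% observed and 14/116 = 12.1% with death or sequelae. Twelve deaths and 5 with sequelae give 5/104 = 4.8% and 17/116 = 14.7%. The order of the arms reverses.

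**The case against.** The strongest reply is that no formal comparison exists to be biased. SAP 2.7.2 states no hypotheses for secondary endpoints, and SAP Table 2-11 shows dashes for between-treatment comparison of sequelae, by cohort and pooled. Mortality, in-hospital mortality and adjudicated malaria-related mortality are summarised separately (SAP 2.8.1). In SAP Table 2-13 deaths and sequelae sit in the same block. Death is also combined with altered consciousness in Day 29 clinical success, which has a Mantel-Haenszel difference and 90% CI. All of this stands and limits the harm. It does not remove it. The objectives are framed as comparisons with artesunate, clinical success does not capture motor or sensory deficits, and two separate tables give no interval for death or sequelae.

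The denominator is also less settled than it may look. A reader might infer that the SAP has fixed a survivor-only analysis. The protocol's exclusion rule points that way, but SAP 2.7.2.3 says only observed FAS data. SAP 2.1 has summaries cover all patients in the population unless otherwise stated, and the by-Day-29 label could admit deficits recorded before death. Further grading details are left to an adjudication charter that is not in the documents. The defect is an unstated denominator and death rule.

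The size may be small. With s_hi = 20% the expected counts at 116 per arm are 116 × 0.055 = 6.4 and 116 × 0.045 = 5.2, about one patient apart.

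**Conclusion.** The concern holds as a gap in the endpoint's definition that can mislead. Under the assumed deaths of 5% and 10%, the observed difference ranges from nil (5.0% against 5.0%) to 2.4 points (7.4% against 5.0%) in favour of the arm with more deaths. That arm is worse by 4.7 to 2.5 points on death or sequelae (14.5% against 9.8% to 12.0%). With a survivor denominator, the effect rests on deaths falling among participants prone to sequelae. That is plausible in severe malaria but is not established in the documents. With deaths kept in the FAS denominator it needs no such assumption. If deaths are few or balanced, the effect is small.

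A reader might go further and infer that the ranking is wrong whenever mortality differs. The first row of the table shows otherwise for a survivor denominator. Nor do the documents supply a mortality forecast. The study-wide trigger of 14 in Protocol Table 3-1, which leaves 13 of 116 (11.2%) below it, mixes deaths with related SAEs. The historical artesunate figures of 0.679 and 0.791 alive without new or worsening complications leave 21% to 32% with death or complications, which cannot be separated.

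**What to change.** In SAP 2.7.2.3:

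1. Keep the existing summary and label its denominator as examined survivors.
2. Show deaths before Day 29 as a row in the same table.
3. Add a supplementary summary, by arm on the FAS, of death or moderate/severe neurological sequelae by Day 29. Give the pooled difference by the Mantel-Haenszel method stratified by cohort, with the 90% CI already specified for clinical success in SAP 2.6.2. State how participants who are alive but not examined are counted.

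Mirror the summary in SAP Table 2-13 on that table's Safety set, and reconcile the at Day 29, by Day 29 and Day 2 labels across the two documents.

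The cost is one extra table and no new data. The downside is that deaths may dominate the composite, which also weighs a moderate deficit such as unilateral hearing impairment equally with death. It can also hide a difference in deaths: 10 deaths with 4 sequelae and 6 deaths with 8 sequelae both give 14/116 = 12.1%. It must therefore be shown next to its components.

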2.7.2.4 Time to event analyses

Time to event will be calculated from the time of first study medication to the date of first event if a patient experiences the event and be censored at the time of last assessment if a patient does not experience the event. Randomization date will be used in the absence of study medication date.

For the following time to event variables, the first visit with the event will be used to calculate the time if a patient experiences the event. If a patient does not experience the event, the time will be censored at the last visit assessment for the specific type of event (such as last sit assessment, etc.) with the exception of date of discontinuation (or death) for time to oral antimalarial therapy.

- Time to *P. falciparum* asexual parasite clearance (PCT) (in hours)
- Time to fever clearance (FCT) (in hours)
- Time to oral antimalarial therapy (in hours),
- Time to recover prostration (in hours) in patients who are prostrated at baseline

Descriptive statistics (mean, standard error, median, quartiles) will be presented using the Kaplan-Meier method by treatment and cohort. Kaplan-Meier curves will be provided by treatment and cohort. For all cohorts pooled, difference for the cipargamin regimen vs artesunate will be evaluated using a log-rank test stratified by cohort (Cohorts 1 and 2 pooled as one cohort). Two-sided 90% CIs for the hazard ratio will be provided.

PCT will be calculated based on *P. falciparum* asexual parasite counts. Patients without parasite clearance for whatever reason will be censored at the time of last parasite assessment. Patients who received any non-study IV antimalarial medication (including IV rescue medication) before parasite clearance will be censored at the first use of antimalarial medication.

Patients who did not have a fever at pre-dose will not be included in the analysis of FCT. Patients without fever clearance for whatever reason will be censored at the time of last temperature assessment. Patients who received any antimalarial medication (including rescue medication) before fever clearance will be censored at the first use of antimalarial medication.

Patients without switching to oral medication for whatever reason will be censored at the time of last study assessment. Patients who received any IV rescue medication will be censored at the first use of IV rescue medication.

Patients who did not have a prostration at pre-dose will not be included in the analysis of time to recover prostration. Patients who do not recover prostration after the IV treatment for whatever reason will be censored at the last study assessment.

Above analysis will be based on FAS.

Tail of KM plots: Since the tail of KM plots after the day of last planned assessment is not reliable due to small numbers of patients at risk, the time to event will be reset to planned last day, i.e. Day 29, regardless of censoring. This principle will be used for relevant tables using the KM method.

